### EQ-5D Quality of Life Questionnaire

The EQ-5D Questionnaire consists of information pertaining to the current health status of the patient at the time of evaluation. The EQ-5D questionnaire measures physical, emotional, and social status. The subject will take between 10 to 15 minutes to complete the test. The form will be completed at each testing session. The subject will provide the best possible answer for that day. The form will be completed preoperatively and postoperatively (3 months, 6 months, 12 months, 24 months, 36 months, 48 months, 60 months, 96 months and 120 months). The form will be completed with minimum or no assistance from the coordinator. The coordinator can clarify a question but will not influence the subject. The subject will provide the best possible answer for that day.

### Constant Score

The Constant Score is a commonly used score of shoulder function.

Collection of this data will allow comparison with both US and European data. The Constant form consists of questions pertaining to shoulder pain, function, and strength. The

**Confidential**

Protocol Date: May 27, 2013  
Amendment 1  
Revision 2

**Ascension Orthopedics**

CP-HRA-002

form will be completed preoperatively and postoperatively (3 months, 6 months, 12 months, 24 months, 36 months, 48 months, 60 months, 96 months, and 120 months) after the patient has regained function.

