## 2.0 Subject Management Table

VISIT INTERVAL	Pre-Op <=180 days Prior to Surgery Day	Day of surgery	1 st Post-Op (1-120 days) 3 Mo Follow Up	Post-Op 6 mo Follow Up	Post-Op 12 mo Follow Up	Post-Op 24 mo Follow Up	Post-Op 36 mo Follow Up	Post-Op 48 mo Follow Up	Post-Op 60 mo Follow Up	Post-Op 96 mo Follow Up	Post-Op 120 mo Follow Up
VISIT	Visit 1	Visit 2	Visit 3	Visit 4	Visit 5	Visit 6	Visit 7	Visit 8	Visit 9	Visit 10	Visit 11
	Screening	Surgery	Post Op	Post Op	Post Op	Post Op	Post Op	Post Op	Post Op	Post Op	Post Op
X-Ray Evaluation	X		X	X	X	X	X	X	X	X	X
MRI Evaluation*	X		X		X	X	X	X	X	X	X
Informed Consent	X										
Inclusion / Exclusion Criteria Worksheet	X										
Medical History	X										
Constant Score	X		X	X	X	X	X	X	X	X	X
WOOS Score	X		X	X	X	X	X	X	X	X	X
EQ-5D Evaluation	X		X	X	X	X	X	X	X	X	X
ASES Score Evaluation	X		X	X	X	X	X	X	X	X	X
Visual Analog Scale for Satisfaction			X	X	X	X	X	X	X	X	X
Visual Analog Scale for Pain	X		X	X	X	X	X	X	X	X	X
Operative Detail		X									
Adverse Event**		X	X	X	X	X	X	X	X	X	X
Subject Withdrawal Forms(as needed)**		X	X	X	X	X	X	X	X	X	X

\* If available    \*\* If applicable

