### Clinical Outcome Forms

All clinical outcome forms will be performed on each study subject at the intervals specified in Section 2, and will be performed per the standard of care at the institution. The research associates/coordinators, or medically qualified designee (not the Surgeon) per their standard of care for patient management purposes, will perform all of the assessments. The following will be assessed: ASES Shoulder Score, Constant Score, WOOS Score, EQ-5D Health Questionnaire, VAS Pain and Satisfaction Scale, and strength and range of motion.

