### ASES Shoulder Score

The ASES Shoulder Score is a functional outcome tool that has been validated for various shoulder conditions (Leggin et al., 1999). This form is commonly used during the clinical process. The ASES Shoulder Score form consists of questions pertaining to patients' satisfaction, function and pain as related to the shoulder. The subject will take between 10 to 15 minutes to complete the test. If the subject requests assistance or a phone consultation is done, completion of the form will be completed with minimum or no assistance from the coordinator. The coordinator can clarify a question but will not influence the subject.

The subject will provide the best possible answer for that day. The form will be completed preoperatively and postoperatively (3 months, 6 months, 12 months, 24 months, 36 months, 48 months, 60 months, 96 months and 120 months).

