### Strength

Strength is given a maximum of 25 points in the Constant Score. The significance and technique of strength measurement has been, and continues to be, the subject of much discussion.

The European Society for Shoulder and Elbow Surgery measures strength according to the following method:

- A spring balance is attached distal on the forearm.
- Strength is measured with the arm in 90 degrees of elevation in the plane of the scapula (30 degrees in front of the coronal plane) and elbow straight.
- Palm of the hand facing the floor (pronation).
- The patient is asked to maintain this resisted elevation for 5 seconds.
- It is repeated 5 times immediately after another.
- The average in pounds or kilograms (lb or kg) is noted.
- The measurement should be pain free. If pain is involved the patient gets 0 points.
- If patient is unable to achieve 90 degrees of elevation in the scapula plane the patient gets 0 points.

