### **Adduction**

Adduction is moving the limb closer to or across the body. Normal range of motion for adduction is 45 degrees. The motion starts at 0 degrees or neutral, which is when the arms are at the side of the body with palms facing forward. 45 degrees is when the upper arm has moved across the front of the body toward the opposite side.

The patient directed forms will be completed with minimum or no assistance from the coordinator. The coordinator can clarify a question but will not influence the subject. The subjects will provide the best possible answer for that day.

As part of the post-operative assessment of each study Subject, the investigator will complete the Constant Score CRF based on source documentation. The Subjects will obtain radiographs, complete the WOOS, EQ-5D, the VAS Scales, ASES Shoulder Evaluation, and update Health History Profile. The center will submit x-rays and MRI's for independent evaluation. All data will be compared with the follow-up data obtained at each study interval.

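### Protocol 6.3 attaches an undefined recovery condition to the post-operative Constant score, in conflict with the unconditional schedule, and so leaves room for selective missing data on a secondary endpoint

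*Protocol*

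**What the plan says.** Protocol 6.3, Constant Score, describes the instrument thus: "The Constant Score is a commonly used score of shoulder function". It names the pre-operative visit and post-operative visits at 3, 6, 12, 24, 36, 48, 60, 96 and 120 months, and ends the sentence with "after the patient has regained function". It does not say what counts as regained function, who decides, or what to do with a subject who has not regained it.

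The other places that govern this score carry no such condition:

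- The Subject Management Table (Protocol 2.0) marks the Constant score at screening and at every post-operative visit without a footnote. Only the MRI row depends on availability, and only the adverse event and withdrawal rows on applicability.
- Protocol 6.3, Clinical Outcome Forms: "All clinical outcome forms will be performed on each study subject at the intervals specified in Section 2".
- Protocol 6.3, closing paragraph after the range-of-motion text: "As part of the post-operative assessment of each study Subject, the investigator will complete the Constant Score CRF based on source documentation".
- SAP 7.10 derives the score for every patient at every visit and tests change from baseline at each post-operative visit with a paired t-test, or a signed-rank test as fallback.

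The Strength paragraph of Protocol 6.3 also says how poor function is scored: "If patient is unable to achieve 90 degrees of elevation in the scapula plane the patient gets 0 points". Pain during the test likewise earns 0 strength points.

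**The concern.** Whether a score is recorded should not depend on the value that it would take. A literal reader of the Constant Score paragraph could leave the form undone for a subject who has not recovered, and that subject would probably have scored low. The scores left in the database would then over-represent good recoveries.

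The SAP would not correct this. Section 7.3 takes the data as observed. The one incompleteness rule for the Constant score in 7.10 concerns the baseline visit, and last-observation-carried-forward appears only for EQ-5D and EQ VAS. A site relying on the phrase might regard the omission as compliant, so the deviation summary in SAP 7.7 might not show it. At stake is the direction of error in the reported mean improvement, which would favour the device.

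**Working it through.** The plan states no figure on this point, so there is none to reproduce. The check is a comparison of texts, followed by an illustration of scale.

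**Comparison of texts**

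| Place | Who and when | Recovery condition |
|---|---|---|
| Protocol 2.0 table | all subjects, Visit 1 and Visits 3–11 | none |
| Protocol 6.3, Clinical Outcome Forms | each subject, each interval | none |
| Protocol 6.3, closing paragraph | each subject, post-operatively | none |
| Protocol 6.3, ASES, WOOS, VAS, EQ-5D | same list of visits | none |
| SAP 7.10 | each patient, each visit | none |
| Protocol 6.3, Constant Score | same list of visits | function regained |

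Only the Constant paragraph has the condition. The scoring rules do not need it: the protocol gives 0 strength points when 90 degrees cannot be reached, and SAP 7.4 gives 0 points to the lowest band of forward flexion and of abduction. Poor function therefore already has a place on the scale.

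**Where it could act.** Protocol 7.0 withdraws a subject whose implant is removed and requires no further visits, so those subjects leave the Constant data whatever the phrase means. The subjects exposed are the unrevised with poor function. The first post-operative window runs from day 1 to day 120 (Protocol 6.3; SAP 7.4), so the 3- and 6-month visits are the most likely place. At 2, 3, 4, 5, 8 and 10 years, the time points named in SAP 5.2, only subjects who never recovered would be exposed.

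**Scale, assumed inputs.** Let q be the share of subjects skipped, A the mean of those scored and B the mean of those skipped. The full mean is (1 − q)A + qB, so

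observed mean − full mean = A − [(1 − q)A + qB] = q(A − B).

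The error in mean change is q times the post-operative gap less q times the baseline gap. It equals q(A − B) only if baselines are similar in the two groups. With an assumed gap of 30 points:

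- q = 5%: 0.05 × 30 = 1.5 points
- q = 15%: 0.15 × 30 = 4.5 points

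**Second illustration.** Suppose that post-operative scores are normal and the lowest fraction q is not taken. The observed mean is then too high by SD × φ(z_q)/(1 − q), where z_q is the q-quantile of the standard normal distribution and φ its density. The documents give no SD; 15 to 25 points is assumed. The last column multiplies by 0.5, for selection that correlates only 0.5 with the score.

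| q | Shift in SD | Shift in points | With correlation 0.5 |
|---|---|---|---|
| 5% | 0.109 | 1.6–2.7 | 0.8–1.4 |
| 10% | 0.195 | 2.9–4.9 | 1.5–2.4 |
| 20% | 0.350 | 5.2–8.7 | 2.6–4.4 |
| 30% | 0.497 | 7.5–12.4 | 3.7–6.2 |

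These rows show how the error grows with the share skipped. They do not estimate what happened in this study.

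**The case against.** The best defence is that the phrase is a loose description of follow-up after recovery. The sentence still lists every visit, nowhere tells a site to defer or omit the form, and on that reading agrees with every other instruction. A site following the schedule would score everyone. This stands in part: there is no express skip rule, and the documents do not show that any score was withheld. It does not remove the conflict, because a site with a poorly functioning subject at a scheduled visit can find support for either course.

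A reader might infer that the missing scores would be concentrated in device failures. The documents do not support this, since subjects whose implant is removed leave follow-up under Protocol 7.0 in any case. Nor do they support reading 1.5 to 4.5 points as the actual bias: the share skipped, the 30-point gap and the similar baselines are all assumed.

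The SAP would also reveal part of the problem. Section 7.1 reports the number of observations and 7.6 the number attending each visit, so a shortfall could be found by subtraction. The reason for it could not.

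Finally, simply striking the phrase could be read as settling a clinical matter. The strength test involves repeated resisted elevation, and the first window opens on day 1. Whether that test suits a subject early after surgery is for the sponsor and investigators.

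**Conclusion.** The point holds as a minor internal contradiction that could bias a secondary endpoint. Followed literally, the condition could leave unrevised subjects with poor function unscored, and the as-observed paired analysis would then overstate mean improvement in the Constant score. The direction follows from the text, provided that unscored subjects would have shown less improvement than those scored. The size cannot be determined from the documents; 1.5 to 4.5 points is an illustration under the stated assumptions. The primary endpoint rests on implant status, device-related complications and chronic dislocation, and is untouched. To infer that sites did skip subjects, or that the Constant results are biased, would go beyond the documents.

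**What to change.** **Protocol 6.3.** Reconcile the Constant Score paragraph with the Subject Management Table, the Clinical Outcome Forms paragraph and the closing paragraph of 6.3, so that recording a Constant score at a scheduled visit does not depend on recovery of function. Leave the clinical suitability of early strength testing to the sponsor and investigators.

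**SAP 7.10.** Report by visit the number of attending, unrevised subjects without a Constant score, and the reason. Add a sensitivity analysis for scores missing because of poor function, with its rule for the missing values written down before those results are examined.

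**Cost.** A small protocol clarification, made through the change procedure in Protocol 20.0 (sponsor and investigator agreement, and ethics approval where it applies), one table and one sensitivity analysis. The protocol dates from May 2013 and the SAP from October 2023, so scores not taken at past visits cannot be recovered. For those visits the table is the more useful step, because it would show how many scores are absent and, where reasons were recorded, whether the phrase played a part.

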### Strength

Strength is given a maximum of 25 points in the Constant Score. The significance and technique of strength measurement has been, and continues to be, the subject of much discussion.

The European Society for Shoulder and Elbow Surgery measures strength according to the following method:

- A spring balance is attached distal on the forearm.
- Strength is measured with the arm in 90 degrees of elevation in the plane of the scapula (30 degrees in front of the coronal plane) and elbow straight.
- Palm of the hand facing the floor (pronation).
- The patient is asked to maintain this resisted elevation for 5 seconds.
- It is repeated 5 times immediately after another.
- The average in pounds or kilograms (lb or kg) is noted.
- The measurement should be pain free. If pain is involved the patient gets 0 points.
- If patient is unable to achieve 90 degrees of elevation in the scapula plane the patient gets 0 points.

## Range of Motion

### **Flexion**

Flexion is when the arm is moving in a straightforward and upward motion. Normal range of motion for flexion of the shoulder joint is 170 to 180 degrees. The motion starts at 0 degrees, or neutral, which is when the arms are at the side of the body with palms facing forward. 180 degrees is when the arms are straight overhead and elbows are by the ears. Anything beyond 180 degrees is considered hyperflexion.

### **Extension**

Extension is when the arm is moving straight backwards. Normal range of motion for extension of the shoulder joint is 50 to 60 degrees. The motion starts at 0 degrees. Shoulder extension is the most powerful shoulder movement.

### **External Rotation**

External rotation occurs when the lower arm rotates outward, away from the body while the elbow remains at the side. Normal range of motion for external rotation is 90 to 100 degrees. For external rotation, 0 degrees is when the upper arm is at the side with the elbows bent 90 degrees. The lower arm is parallel to the floor, and the hand is pointing forward.

### **Internal Rotation**

Internal rotation occurs when the lower arm moves inward, toward the body while the elbow remains at the side. Normal range of motion for internal rotation is 80 to 90 degrees. For internal rotation, 0 degrees is when the upper arm is at the side with the elbows bent 90 degrees. The lower arm is parallel to the floor, and the hand is pointing forward.

### **Abduction**

Abduction is when the arm is moved outward from the side of the body. Normal range of motion for abduction of the shoulder joint is 170 to 180 degrees. The motion starts at 0 degrees, which is when the arms are at the side of the body with palms facing forward. 180 degrees is when the arms are straight overhead and elbows are by the ears.

### **Adduction**

Adduction is moving the limb closer to or across the body. Normal range of motion for adduction is 45 degrees. The motion starts at 0 degrees or neutral, which is when the arms are at the side of the body with palms facing forward. 45 degrees is when the upper arm has moved across the front of the body toward the opposite side.

The patient directed forms will be completed with minimum or no assistance from the coordinator. The coordinator can clarify a question but will not influence the subject. The subjects will provide the best possible answer for that day.

As part of the post-operative assessment of each study Subject, the investigator will complete the Constant Score CRF based on source documentation. The Subjects will obtain radiographs, complete the WOOS, EQ-5D, the VAS Scales, ASES Shoulder Evaluation, and update Health History Profile. The center will submit x-rays and MRI's for independent evaluation. All data will be compared with the follow-up data obtained at each study interval.

### **6.4 Radiograph Requirements: X-Ray and MRI**

The shoulder radiographic views will consist of a true anterior-posterior in the scapular plane, internal and external rotation, axial lateral and an axillary lateral view. The patient will be placed in a shoulder harness to maintain 30 degrees of scapular plane during the examination or subjects may be radiographed supine with wedge support. Patients may come to the office with shoulder radiographs already completed at their first clinical visit.

Additional radiographs may be needed if the radiographs are of poor quality and/or do not provide adequate information on the humeral head.

Radiographs will be completed at the following time periods: pre-operatively within 180 days of surgery and post-operatively: 3 months, 6 months, 12 months, 2 years, 3 years, 4 years, 5 years, 8 years and 10 years. The following will be assessed on the radiographic evaluation: loosening of the humeral component, osseous structures, anatomic alignment, condition of the glenoid and joint congruity.

The patient will not need radiographs if they have had a revision surgery and/or they are lost to follow-up. Radiographs are obtained at the pre- and post-operative intervals, as designated on the Subject Management Schedule.

Radiographic evaluation parameters are provided below. All radiographs are submitted to the Sponsor after the scheduled visit. To avoid potential bias, an independent radiographic reviewer (IRR) will evaluate all radiographs. The reviewer will complete the radiographic evaluation forms and forward them to the Sponsor for entry into the database. Data from the IRR radiographic evaluation will be used for determining the radiographic success criteria.

### **General Instructions**

- All effort should be made to utilize the same X-ray machine with the same settings across time periods for each individual. To ensure consistency in quality of the radiographs, it is recommended the kVp, mAs, FFD, and tube angles must remain the same for a given patient at all time periods.
- Radiographs should be of adequate quality (not over or under exposed).
- All radiographs should be performed using digital DICOM 3 uncompressed format. Digital files should be recorded onto the Study CD labeled with the required patient and visit identifiers.
- All actions must be taken by the site to anonymize the radiographic images.

**Confidential**

Protocol Date: May 27, 2013  
Amendment 1  
Revision 2

**Ascension Orthopedics**

CP-HRA-002

- Digital images must be submitted at 100% scale or true to size
- For film, the film size should be appropriate to the size of the subject
- Left or right lead markers must be utilized without superimposition of pertinent anatomy.

**AP SHOULDER RADIOGRAPH ACQUISITION**  
**External Rotation, Neutral Rotation, and Internal Rotation**  
**Scapular Plane**

View	kVp	mAs	FFD	Film Size	Centering	Patient Instruction
AP External	70-80	10	Between 40 and 48 inches (100-120 cm)	24 X 30 cm crosswise	The central ray should be perpendicular to film centered to coracoid process	The patient may be examined in the erect or supine position. The erect position is recommended whenever possible so that the patient's body position can be adjusted to require little or no manipulation of the arm.
Neutral Rotation	70-80	10	Between 40 and 48 inches (100-120 cm)	24 X 30 cm crosswise	The central ray should be perpendicular to film centered to coracoid process	The patient may be examined in the erect or supine position. The erect position is recommended whenever possible so that the patient's body position can be adjusted to require little or no manipulation of the arm.
AP Internal	70-80	10	Between 40 and 48 inches (100-120 cm)	24 X 30 cm crosswise	The central ray should be perpendicular to film centered to coracoid process	The patient may be examined in the erect or supine position. The erect position is recommended whenever possible so that the patient's body position can be adjusted to require little or no manipulation of the arm.

**AP Shoulder**

- Place the patient in the erected position.

**Confidential**

Protocol Date: May 27, 2013

Amendment 1

Revision 2

**Ascension Orthopedics**

CP-HRA-002

- Adjust the patient's body to center the film to the coracoid process. Rotate the patient enough to place the blade of the scapula parallel with the plane of the film.

#### External Rotation

[figure not shown]
- Ask the patient to turn the palm of their hand forward.
- Abduct the arm slightly and adjust it so that the coronal plane of the epicondyles is parallel with the plane to the film.

#### Neutral Rotation

- Ask the patient to rest the palm of the hand against his thigh.

#### Internal Rotation

- Ask the patient to flex their elbow, rotate the arm internally and rest the back of the hand on his hip.
- Adjust the arm to place the coronal plane of the epicondyles perpendicular to the plane of the film.
- If this positioning is too painful for internal rotation, the patient may turn away from the film.

LATERAL SHOULDER RADIOGRAPH ACQUISITION Axial Lateral and Axillary Lateral					
kVp	mAs	FFD	Film Size	Centering	Patient Instruction
		Between 40 and 48 inches (100-120 cm)	18 X 24 cm lengthwise	Direct the central ray at angle of 5 to 15 ° toward the elbow.	Seat the patient at the end of the table with the shoulder centered to the midline of the table. The patient should be seated on a stool or chair high enough to enable him to extend the affected shoulder over the cassette.

